## Summary and Schema

**Treatment Arm:** One course of treatment (84 days) will consist of high dose (600,000 IU/kg) bolus IL-2 administered intravenously every 8 hours beginning on day 1 and day 15 (maximum of 14 doses per cycle of administration); and hydroxychloroquine (HCQ) orally started two weeks prior to IL-2 infusions (+/- 1 day) [to allow for weekends/holidays etc] and continued while able to take oral medication throughout all courses. For patients with evidence of stable disease or response up to three courses can be administered as shown below. Patients will be administered 600mg/d of HCQ at all sites in a total group of 21.

Drug	Course 1								
	Days:								
	-14	1	15	29	43	57	71	84	
Hydroxychloroquine	X							-----	X
IL-2		X	X						
Biomarker	X	X	X						

Drug	Course 2							
	Days:							
	85	99	113	127	141	155	168	
Hydroxychloroquine	X						-----	X
IL-2	X	X						
Biomarker	X							

Drug	Course 3							
	Days:							
	169	183	197	211	225	239	252	
Hydroxychloroquine	X						-----	X
IL-2	X	X						
Biomarker	X							

### **Agents**

- **Hydroxychloroquine** oral at 600 mg/d throughout the treatment. Continuous oral administration will be initiated prior to the first dose (day -14), given a minimum of 14 days (maximum of 21 days) prior to initiation of the first dose of IL-2 and then daily or twice a day throughout all three treatment courses.
- **Aldesleukin (IL-2)** 600,000 IU/kg IV bolus q 8 hrs beginning on day 1 and day 15 (maximum 14 doses per cycle).

### **Response Assessment**

- Patients will undergo CT scans at week 8 (+/- 1 week) and week 12 (+/- 1 week), then after both subsequent courses (every 10-12 weeks). After the final course (week 36), patients will undergo CT scan evaluation every 12 weeks (+/- 2 weeks) for up to one year or until tumor progression (whichever comes first). If additional scans are performed for clinical reasons, the study schedule may be altered to perform the requisite scans at a more acceptable time point. The change in timing of study scans must be approved by the local PI and documented. For patients who have not shown progression at the end of one year, response will be captured during follow-up for survival, which will be done on all patients via telephone contact and medical record review.
- Hydroxychloroquine will continue daily until documented disease progression or 12 weeks following documented complete response.
- Patients with evidence of tumor shrinkage may receive up to 3 courses of IL-2 therapy. Course 2 will start on or within 2 weeks following day 85 and follow the same schedule as in Course 1. Course 3 can start within 2 weeks of completion of course 2. Patients not receiving IL-2 during course 2 who have some evidence of tumor shrinkage by week 24 can receive a 2nd course of IL-2 beginning within 2 weeks of week 25.
- Patients with no evidence of progression by RECIST 1.1 criteria may receive continued treatment with hydroxychloroquine through one year of initiation of HCQ treatment (Day -14) or until disease progression.
- Patients with progressive disease by RECIST 1.1 criteria will be taken off-study.
- Both responding and non-responding patients will be followed until death or final closure of the study (6.4.2). Attention will be paid to the time of disease progression and time of initiation of alternate therapies.

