### **6.4 Response Assessment/ Duration of Therapy**

Patients will undergo CT scans at week 8 and week 12 (+/- 1 week) following initiation of IL-2 therapy and then after each course (every 10-12 weeks). After the final course (week 36), patients will undergo CT scan evaluation every 12 weeks (+/- 2 weeks) for up to one year or until tumor progression (whichever comes first). If additional scans are performed for clinical reasons, the study schedule may be altered to perform the requisite scans at a more acceptable time point. The change in timing of study scans must be approved by the local PI and documented. For patients who have not shown progression at the end of one year, response will be captured during follow-up for survival (explained below).

Patients with evidence of tumor shrinkage with all lesions measurable and evaluable may receive up to 3 courses of IL-2 therapy. Course 2 will start on or within 2 weeks following day 85 and follow the same schedule as in Course 1. Course 3 can start within 2 weeks of completion of Course 2. Patients not receiving IL-2 during course 2 with tumor shrinkage by week 24 can receive a 2nd course of IL-2 beginning within 2 weeks of week 25.

Patients with no evidence of progression by RECIST 1.1 criteria may receive continued treatment with hydroxychloroquine through one year of initiation of HCQ treatment (Day -14) or until disease progression.

Tumor response will be assessed by the NCI’s Response Evaluation Criteria in Solid Tumors (RECIST) 1.1 guidelines. Patients will undergo tumor evaluation with physical exam and CT scans at week 8 (+/- 1 week) and week 12 (+/- 1 week), then after each course (every 10-12 weeks). After the final course (week 36), patients will undergo CT scan evaluation every 12 weeks (+/- 2 weeks) for up to one year or until tumor progression (whichever occurs first). If additional scans are performed for clinical reasons, the study schedule may be altered to perform the requisite scans at a more acceptable time point. The change in timing of study scans must be approved by the local PI and documented. For patients who have not shown progression at the end of one year, response will be captured during follow-up for survival, which will be done on all patients via telephone contact and medical record review. Patients with progressive disease by RECIST 1.1 criteria will be taken off study.

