- e.** ECHO or MUGA will be performed at baseline. ECHO will be performed prior to start of each new course only if clinically indicated (section 10.3.3).
- f.** Screening labs to include CBC w/differential, CMP (creatinine, BUN, albumin, total protein, glucose, electrolytes [Na, K, Cl, HCO3], liver function tests [total bilirubin, ALP, AST, ALT]), direct bilirubin, calcium, phosphorus, LDH, TSH, PT, PTT, HIV, Hep B and C, Pregnancy test for women of childbearing potential.
- g.** Proteinuria level must be checked prior to each cycle of IL-2.
- h.** Outpatient labs to include CBC w/differential, CMP (creatinine, BUN, albumin, total protein, glucose, liver function tests [total bilirubin, ALP, AST, ALT], electrolytes [Na, K, Cl, HCO3]), LDH, CPK, amylase, and lipase.
- i.** Inpatient labs to include CBC w/differential, CMP (creatinine, BUN, albumin, total protein, glucose, liver function tests [total bilirubin, ALP, AST, ALT], electrolytes [Na, K, Cl, HCO3]), direct bilirubin, calcium, magnesium, phosphorus, LDH, CPK, amylase, and lipase.
- j.** Outpatient labs to include CBC w/differential, CMP (creatinine, BUN, albumin, total protein, glucose, liver function tests [total bilirubin, ALP, AST, ALT], electrolytes [Na, K, Cl, HCO3]), amylase, and lipase
- k.** Patients with no evidence of progression by RECIST 1.1 criteria may receive continued treatment with hydroxychloroquine through one year of initiation of HCQ treatment (Day -14) until disease progression.
- l.** IL-2 every 8 hours on days 1-5 (or 6) and 15-19 (or 20) (maximum 14 doses per 5 day cycle). Dependent upon when Dose 1 is administered on Day 1/Day 15, Dose 14 could require hospitalization on Day 6/Day 20.
- m.** HCQ daily dosing starting on Day -14 (minimum of 14 days, plus a window of + 7 days if needed)
- n.** See Table 6 for sampling schedule. Cycle 2 draws will only be done in Course 1.
- o.** Blocks or slides will be sent within 4 weeks after enrollment.
- p.** Subjects will be evaluated with physical examination ~30 days (28-42 days) after being removed from study for any reason.

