**SUBJECT DRUG ADMINISTRATION DIARY FOR HYDROXYCHLOROQUINE TABLETS**

Protocol ID: UPCI 11-080	Study Drug: Hydroxychloroquine (HCQ)
Subject Identification #:	Study Drug Start Date:
Course #: N/A (Day 267 to Day 351)	Course Start Date: N/A

Study Day	Date	AM DOSE _____200 mg tablet(s)		PM DOSE _____200 mg tablet(s)		Comments	Missed Doses
		# pills taken	Time taken	# pills taken	Time taken		
267							
268							
269							
270							
271							
272							
273							
274							
275							
276							
277							
278							
279							
280							
281							
282							
283							
284							
285							
286							
287							
288							
289							
290							
291							
292							
293							

294							
SUBJECT DRUG ADMINISTRATION DIARY FOR HYDROXYCHLOROQUINE TABLETS							
Protocol ID: UPCI 11-080				Study Drug: Hydroxychloroquine (HCQ)			
Subject Identification #:				Study Drug Start Date:			
Course #: N/A (Day 267 to Day 351)				Course Start Date: N/A			
Study Day	Date	AM DOSE ____200 mg tablet(s)		PM DOSE ____200 mg tablet(s)		Comments	Missed Doses
		# pills taken	Time taken	# pills taken	Time taken		
295							
296							
297							
298							
299							
300							
301							
302							
303							
304							
305							
306							
307							
308							
309							
310							
311							
312							
313							
314							
315							
316							
317							
318							
319							
320							
321							

322							
-----	--	--	--	--	--	--	--

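### Two hydroxychloroquine duration rules apply to the same patient with no stated precedence; for complete responders the permitted end of dosing differs by up to 30 weeks

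*Combined protocol and SAP*

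**What the plan says.** The Response Assessment list in the Summary contains two statements on how long HCQ is given.

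- **12-week rule:** "Hydroxychloroquine will continue daily until documented disease progression or 12 weeks following documented complete response". It is worded as a directive and has no calendar limit.
- **One-year rule**, a few bullets later: patients without RECIST 1.1 progression "may receive continued treatment with hydroxychloroquine through one year of initiation of HCQ treatment (Day -14) or until disease progression". It is worded as a permission and makes no exception for CR.

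Elsewhere only the one-year rule appears. Section 6.4 says "Patients with no evidence of progression by RECIST 1.1 criteria may receive continued treatment with hydroxychloroquine through one year". Footnote k of the Schedule of Events (Appendix B) has "through one year of initiation of HCQ treatment (Day -14) until disease progression", without the word that separates the two limits in the other places. The patient diary in Appendix F is laid out to Day 351.

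A third description ties HCQ to the IL-2 courses. The Agents section of the Summary has it given "daily or twice a day throughout all three treatment courses", the Summary's treatment-arm paragraph likewise covers all courses, and section 6.2 says up to three courses. The list of reasons for ending treatment in section 6.4.2 does not include CR. No section ranks these statements.

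**The concern.** A complete responder has, by definition, no evidence of progression, so both rules reach the same patient and give different end dates. The 12-week rule is found only in the Summary. A site working from section 6.4, the Schedule of Events and the diary would not meet it, while a site working from the Summary would. Practice could therefore differ between sites; that is an inference from the text, not something the documents report.

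The conflict is wider than CR. For a non-progressing patient without CR, the 12-week sentence continues HCQ until progression with no time cap, while the other rule stops at one year.

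At stake is how long the combination is actually given. That bears on duration of response (section 10.5), progression-free survival (section 10.8) and toxicity from prolonged exposure, and on whether a later IL-2 course is accompanied by HCQ dosing.

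**Working it through.** **Inputs.** HCQ starts on Day -14. The one-year limit runs from Day -14. The 12-week clock is 12 × 7 = 84 days from documented CR. Courses run Days 1–84, 85–168 and 169–252 (Summary schema). CT scans fall at weeks 8 and 12 and after each later course. Confirmation of CR comes at least 4 weeks after criteria are first met (section 10.4). All days below are nominal and ignore the visit windows.

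**The plan's own end date.** -14 + 365 = Day 351, the last day named in the diary. Counting doses without a Day 0 gives the same day: 14 lead-in days + 351 = 365. The diary therefore follows the one-year rule.

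**Comparison for complete responders.** 12-week end = CR day + 84. Gap = 351 - (CR day + 84).

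| CR documented | 12-week rule ends HCQ | One-year rule permits HCQ to | Gap |
|---|---|---|---|
| Week 8 (Day 56) | Day 140 | Day 351 | up to 211 days (30 weeks) |
| Week 12 (Day 84) | Day 168 | Day 351 | up to 183 days (26 weeks) |
| End of course 2 (Day 168) | Day 252 | Day 351 | up to 99 days (14 weeks) |
| End of course 3 (Day 252) | Day 336 | Day 351 | up to 15 days |
| Day 336 | Day 420 | Day 351 | -69 days |

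The rules coincide only for a CR documented on Day 351 - 84 = 267. After that, the 12-week rule runs past the one-year limit.

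**Course 3.** It starts from Day 169. A CR documented at week 8 ends HCQ 169 - 140 = 29 days earlier. A CR documented at week 12 ends it on Day 168, the day before. If course 3 is then given, HCQ dosing has stopped before it begins, against the Agents section.

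**What starts the clock.** The Summary does not say whether CR counts as documented when criteria are first met or when confirmed. If confirmation counts:

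- CR first met at week 8 and confirmed at week 12: 84 + 84 = Day 168, a gap of up to 26 weeks, still before course 3.
- CR first met at week 12 and confirmed four weeks later: 84 + 28 + 84 = Day 196, a gap of up to 351 - 196 = 155 days (22 weeks), and HCQ would reach into course 3.

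**Link to the primary count.** The clock starts only after CR is documented, and the 4-week minimum for confirmation fits inside the 12 weeks. The nearest link is the clause in section 10.3 that scores a partial response of more than 90%, sustained for over a year, as CR. If first met at week 8, it must last beyond 56 + 365 = Day 421, which is 421 - 351 = 70 days after the one-year limit. The 12-week sentence would keep such a patient on HCQ over that period; the one-year rule would not.

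**The case against.** The best defence is that the rules can be nested. The 12-week sentence is specific and directive; the one-year sentence is general and permissive. On that reading, a CR-specific stop sits inside a one-year maximum and nothing is contradictory. It is a workable reading, but the documents do not state it. The body text, schedule and diary carry no CR exception, and the reading still leaves the Agents section unmet for an early CR that goes on to course 3. It also does not settle the position of patients without CR.

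Three parts of the defence stand and limit the point:

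- **The gap is a maximum.** The one-year rule allows HCQ to Day 351 but does not require it. A reader might take 30 weeks as a fixed difference for every complete responder. It is the upper end for the earliest CR, and it shrinks to 15 days by the end of course 3.
- **Course 3 is optional and HCQ clears slowly.** No section requires course 3 after CR. Section 2.9 gives a half-life of 40 to 45 days, and section 6.3.1.1 relies on it to tolerate missed doses. Over 29 days, simple first-order decay (my assumption) leaves 0.5^(29/40) = 60% to 0.5^(29/45) = 64%. A reader might infer an IL-2 course without HCQ; the text supports only a course without HCQ dosing.
- **Few patients are involved.** The planning case in section 13.4 is 5 CRs in 39.

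**Conclusion.** The inconsistency is real and in current text: two stated duration rules cannot both govern the same patient, and no precedence is given. For complete responders the permitted end of HCQ differs by up to 30, 26 or 14 weeks, or 15 days, according to when CR is documented, and the order reverses after Day 267. For other non-progressing patients it is no cap against one year. These figures rest on nominal visit days and on CR counting as documented at the scan named.

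Because complete responders are the events in the primary endpoint, a reader might infer that the primary CR proportion is compromised. The documents do not support that. Stopping HCQ after a documented CR does not remove it from the count, and no sample-size figure or monitoring boundary depends on the rule. Through the sustained-partial-response clause the effect on the primary count is at most indirect. The direct effects are on HCQ exposure, response duration, progression-free survival and late toxicity. It should be corrected, since it changes what patients are given and is cheap to settle.

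**What to change.** - Reconcile the Summary (treatment-arm paragraph, Agents, Response Assessment), sections 6.2, 6.4 and 6.4.2, and footnote k of Appendix B to one HCQ duration rule, covering both complete responders and other non-progressing patients. Which rule applies is the sponsor's decision; this review takes no position on it.
- If a clock from CR is kept, state whether it starts when criteria are first met or when CR is confirmed under section 10.4, and how it treats a sustained partial response of more than 90% that is later scored as CR.
- State whether HCQ dosing accompanies an IL-2 course given after CR.
- Report HCQ start, stop and total duration for each complete responder, so that response duration and progression-free survival can be read against actual exposure.

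The cost is amendment wording, alignment of the diary if the end day changes, and one listing in the report. Sample size and primary analysis are unaffected.

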## 1.0 OBJECTIVES

We hypothesize that IL-2 administration enhances systemic autophagy, limiting the effectiveness of immune effectors and that coadministration of the autophagy inhibitor hydroxychloroquine will enhance response, diminish toxicity other than possibly GI toxicity, and increase the ability to administer IL-2.

### 1.1 Primary:

1. Estimate the proportion of patients with metastatic RCC treated with IL-2 combined with hydroxychloroquine at 600 mg/d who experience a clinical complete response.

### 1.2 Secondary:

2. Compare the distribution of clinical responses, overall survival and progression-free survival of patients with metastatic RCC treated with IL-2 combined with hydroxychloroquine to *the published response of patients treated with high dose IL-2 alone (Proclaim database and publication)*.
3. Characterize the safety and toxicity of IL-2 combined with hydroxychloroquine:
  - a. Number of doses of IL-2 administered during the first course of therapy
  - b. Toxicity after the scheduled 9th dose of IL-2
  - c. Frequency of grade III and IV or unexpected or rare toxicities [Section 9.5]
4. Determine the relationship between laboratory parameters (Sections 7.2-7.5) evaluated at baseline and during treatment and toxicity, clinical response, and survival.
5. Evaluate the utility of known prognostic criteria for RCC patients on clinical outcome. (1). Pretreatment features associated with a shorter survival are low Karnofsky performance status; (<80%), high serum lactate dehydrogenase (> 1.5 times upper limit of normal), low hemoglobin (< lower limit of normal), high "corrected" serum calcium (> 10 mg/dL), and absence of prior nephrectomy (see 13.2.4).

## **2.0 BACKGROUND AND RATIONALE**

### **2.1 Treatment of RCC- Background**

In 2010, it is estimated that there will be 35,710 new cases of kidney cancer and approximately 12,480 kidney cancer-specific deaths in the United States (2). One-third of patients have metastatic disease at the time of diagnosis. Two recent randomized studies in metastatic RCC patients have shown survival benefit of nephrectomy and cytokine therapy over cytokine therapy alone (3, 4). For this reason, and for symptom control, many patients with metastatic disease at presentation undergo nephrectomy as a component of their standard care. The prognosis for recurrent or metastatic renal cell carcinoma is poor. Median survival was 10-13 months prior to the development of agents targeting the VEGF and mTOR pathways, and is now approximately 2 years in good- and intermediate-prognosis patients (5) and 5-year survival is less than 5%. These figures underscore the need for effective systemic therapy in this disease.

Medical treatment for RCC has primarily focused on biological therapies designed to mobilize immune effector cells that recognize and destroy cancer cells (3-9). Several randomized studies have suggested that interferon produces modest antitumor benefit in patients with advanced renal cancer, while IL-2 has received FDA approval due to its ability to produce durable responses, albeit in only a minority of patients. Tumor infiltrating lymphocytes are often NK cells, which, when present in high numbers, are associated with improved prognosis (see below).

### **2.2 High-dose IL-2 Therapy for Patients with RCC**

Investigations of IL-2 (Aldesleukin, Chiron) in patients with RCC were initiated by our group [Surgery Branch] at the NCI in the mid-1980s, and continued there and within the Cytokine Working Group. Initial studies evaluated high-dose bolus IL-2 therapy in combination with the infusion of autologous lymphocytes activated *ex vivo* in IL-2 (lymphokine-activated killer or LAK cells) (10, 11). While dramatic and durable responses were reported in some patients, subsequent studies found the efficacy of high-dose bolus IL-2 alone to be equivalent to that of the combination of IL-2 and LAK cells, prompting the abandonment of this more complex cellular therapy component.

In 1992, high-dose bolus IL-2 was approved by the FDA for the treatment of patients with metastatic renal cell cancer based on data presented on 255 patients entered onto 7 phase II clinical trials (8, 12). In these studies, 600,000-720,000 IU/kg of recombinant human IL-2 was administered by 15-minute infusion every 8 hours x 14 doses, thereby constituting a course of therapy. Patients received a course of therapy, consisting of two 5-day treatment cycles separated by 5-9 days of rest (maximum of 28 doses) (cycle 1A/1B). Courses were repeated every 8-12 weeks in stable or responding patients. Although 35% of patients received 720,000 IU/kg of IL-2 per dose and the remainder received 600,000 IU/kg per dose, the median cumulative amount of IL-2 administered was the same in both groups, since patients receiving 720,000 IU/kg per dose tolerated fewer IL-2 doses. Ninety-six percent of these patients had an ECOG performance status of 0 or 1, 85% had undergone a nephrectomy prior to starting IL-2 therapy, none had received prior immunotherapy, and the median time from diagnosis to treatment was 8.5 months.

Objective responses were seen in 37 of the 255 patients (RR 15%). There were 17 (7%) complete responses (CRs) and 20 (8%) partial responses (PRs). Fourteen of the responding patients (38%) began therapy with tumor burdens  $>50 \text{ cm}^2$  on pretreatment scans and 60% of PRs had  $>90\%$  regression of all measurable disease. The median duration of response was 54 months for all responders, 20 months for PRs and has not yet been reached for CRs. The median survival was 16 months for all 255 patients.

Follow-up data on these patients has now been accumulated through June 2010, with a median follow-up of over 10 years. Although some late relapses are still being observed, the response duration curve appears to have leveled off after the 30 month time point and 60% of complete responders remain in remission. In addition, 4 PRs who underwent surgical resection of residual disease while still in response remain alive and disease-free at a minimum of 65+ months. Therefore, many CRs remaining free from progression for more than thirty months and those PRs resected to NED after a response to high-dose IL-2 are unlikely to progress and may actually be cured. Thus, although the response rate to high-dose bolus IL-2 is modest, it can produce meaningful benefit in a small proportion of patients. Means to enhance this response are clearly in order.

The High Dose Aldesleukin "Select" trial was conducted to prospectively assess the ability of histologic, immunohistochemical and other pathologic tumor features to predict overall response rate and other outcomes (McDermott et al. 2011). This study enrolled 123 patients between November 2006 and July 2009, at many of the same Cytokine Working Group Institutions participating in the present study. Patients received high dose aldesleukin at a standard dose and schedule, and with standard recommendations for treatment modification for toxicity (Schwartzentruber 2001). The High Dose Aldesleukin "Select" study therefore represents a contemporaneous population of patients with similar baseline characteristics and aldesleukin treatment with which to compare to the current study with regard to outcomes and toxicity."

In that trial, overall response rate was 25% by independent review (95% CI 17.5-33.7) and 28% by investigator review (as to be performed in this study) (95% CI 20.5-37.3%). The distribution of MSKCC 2002 risk was 19/70/11% (Good/Int/Poor). Median PFS was 4.3 months (95% CI 2.5-4.7 mo) (comparable to prior studies where about half the patients progressed on the first scan). As seen previously, there was a "tail" of durable progression-free survival (PFS rate at 3 years was 11%). Median overall survival was 42.8 months (95% CI 35.6-51.9 months). Median duration of response was 20.6 months (CI 6.9-42.7 mo)

